### **6.5.2.2 Serious Adverse Events**

Treatment-emergent serious AEs (TESAE) will be summarized. Number and proportion of subjects experiencing a treatment-emergent serious AE will be presented by system organ class and preferred term overall and for each treatment group.

An overall summary of the total number of TESAEs reported, the number and proportion of subjects experiencing at least one TESAE, at least one severe TESAE, at least one TESAE related to the study treatment, at least one TESAE leading to treatment discontinuation, a TESAE leading to death, at least one TESAE requiring supplemental oxygenation, at least one TESAE requiring mechanical ventilation and at least one TESAE requiring ECMO will also be presented.

Treatment-emergent serious AEs (TESAE) related to study treatment will also be summarized. Number and proportion of subjects experiencing a treatment-emergent serious AE related to study treatment will be presented by system organ class and preferred term overall and for each treatment group.

An overall summary of TESAEs related to study treatment that includes the total number of TESAEs related to study treatment reported, the number and proportion of subjects experiencing at least one TESAE related to study treatment, at least one severe TESAE related to study treatment, at least one TESAE related to study treatment leading to treatment discontinuation, a TESAE related to study treatment leading to death, at least one TESAE related to study treatment requiring supplemental oxygenation, at least one TESAE related to study treatment requiring mechanical ventilation and at least one TESAE related to study treatment requiring ECMO will also be presented.

All SAEs will also be listed (Section 7, Listing 9).

A separate listing for deaths will be also provided (Section 7, Listing 10).

### 6.5.3 Laboratory Parameters

Laboratory data will be transferred electronically by Covance central lab. For all laboratory parameters, results at each visit and change from screening will be summarized overall and by treatment group using descriptive statistics (N, mean, median, standard deviation, Q1, Q3, minimum and maximum).

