#### **4.4.2.1. Liver Injury**

Discontinuation of study treatment for abnormal liver tests should be considered by the Investigator when a patient meets one of the conditions mentioned below or if the Investigator believes that it is in the best interest of the patient.

- Discontinue the study treatment if  $\text{AST/ALT} > 8 \times \text{ULN}$
- Discontinue the study treatment if  $\text{AST/ALT} > 3 \times \text{ULN}$  and serum total bilirubin levels  $> 2 \times \text{ULN}$  (Hys law)
- Discontinue the study treatment if repeat  $\text{AST/ALT} > 5 \times \text{ULN}$

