### **8.5. Safety Analysis**

Safety variables include incidence of AEs (or TEAEs), laboratory test results, and vital signs. All safety analyses will be based on the Safety Population. No formal statistical analysis of the safety data will be performed.

Adverse events will be coded according to MedDRA, version 23.0 released 19 Apr 2020 (exclusively meant for COVID-19) or later.

The number and percentage of patients with TEAEs, SAEs, TEAEs related to study treatment, SAEs related to study treatment, TEAEs leading to treatment discontinuation, TEAEs leading to study discontinuation, and TEAEs leading to death will be summarized by SOC, preferred term (PT), and treatment group. In addition, the severity of TEAEs and relationship to study treatment will be summarized by SOC, PT, and treatment group.

The AE summary tables will include counts of patients. Therefore, if a patient experiences more than 1 episode of a particular AE, the patient will be counted only once for that event. If a patient has more than one AE that is coded to the same PT, the patient will be counted only once for that PT. Similarly, if a patient has more than 1 AE within a SOC, the patient will be counted only once in that SOC.

Test values and change from baseline will be summarized descriptively by treatment group for specific laboratory test results and vital signs. Where applicable, shift tabulations will be presented for specific laboratory test results by treatment group. Where applicable, number and frequency of clinically significant abnormal values for specific laboratory test results will be presented.

Pregnancy test results and patients with confirmed positive pregnancy test result will be listed.

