## 1 INTRODUCTION

The purpose of this statistical analysis plan (SAP) is to present the statistical methodology that will be used for the final analysis of DalCor Pharmaceuticals DAL-401. This plan also provides a description of the tables, figures and listings that will be included in the final statistical report. It is based on the protocol dated 22-OCT-2020 and on the annotated case report form (CRF) version 1.0. In case of differences in terms of descriptions or explanations between the SAP and the clinical protocol, the SAP will supersede the protocol. Any deviation to this SAP would be reported in the statistical report.

Since the protocol was developed and discussed with the regulatory authorities, a greater understanding of COVID-19 and clinical trials in COVID-19 has emerged. New variants have also been observed and their clinical course needs to be taken into consideration. Based on this emerging knowledge, a higher emphasis will be placed on viral load analyses when interpreting the data and deciding on POC in this study. Less emphasis will therefore be placed on the current primary endpoint of Patient Reported Outcomes and endpoints that look at changes in symptoms of COVID-19. Certain symptoms such as loss of taste and loss of smell as well as cough are chronic symptoms which may not resolve over the course of a 28-day study. In view of this the endpoints evaluating symptoms will not include taste, smell or cough in some analyses.

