Table 3.2.10	Summary of treatment emergent serious adverse events (TESAE) related to study treatment by preferred term and system organ class, Safety population
3.3 Laboratory variables	
Table 3.3.1	Summary of hematology, Safety population
Table 3.3.2	Summary of biochemistry, Safety population
3.4 Other safety parameters	

Table 3.4.1	Summary of vital pulse rate (bmp), Safety population
Table 3.4.1	Summary of vital SpO2 (%), Safety population
Table 3.4.2	Summary of vital SpO2 (%) in categories, Safety population

Figures	
Figure 1	Subject Disposition (flow chart)
Figure 2	Cumulative incidence curve for sustained clinical resolution (excluding cough, sense of smell and taste), ITT population
Figure 3	Cumulative incidence curve for sustained clinical resolution (excluding cough, sense of smell and taste), PP population – Sensitivity analysis
Figure 4	Cumulative incidence curve for sustained clinical resolution (excluding cough, sense of smell and taste) with last observation carried forward, ITT population – Sensitivity analysis
Figure 5	Plot of mean change from baseline in log10 viral load (saliva) with 80% CI at each study visit, ITT population
Figure 6	Plot of mean change from baseline in log10 viral load (nasal swab) with 80% CI at each study visit, ITT population
Figure 7	Cumulative incidence curve for sustained clinical resolution, ITT population
Figure 8	Plot of mean change from baseline in COVID-19 total symptom score with 80% CI at each study visit, ITT population
Figure 9	Frequency distribution plot of WHO clinical outcome scale at each study visit, ITT population

Listings	
Listing 1	Subject disposition
Listing 2	Datasets analyzed
Listing 3	Protocol deviations
Listing 4	Demographics
Listing 5	Concomitant medications
Listing 6	Study medication administration
Listing 7	COVID-19 related symptoms and endpoints
Listing 8	WHO clinical outcome scale
Listing 9	Adverse events and serious adverse events
Listing 10	Deaths

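### SAP 6.5.3 keeps only per-analyte laboratory summaries and drops the shift tables and abnormal-value counts in Protocol 8.5, so no per-arm count of patients crossing the protocol's AST/ALT limits is planned

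*SAP*

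**What the plan says.** **Protocol 8.5**, repeated in the synopsis safety analysis, plans three laboratory outputs by treatment group: descriptive summaries of values and changes; shift tables ("Where applicable, shift tabulations will be presented for specific laboratory test results by treatment group"); and, with the same qualifier, counts of abnormal results ("number and frequency of clinically significant abnormal values for specific laboratory test results will be presented").

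**Protocol 4.4.2.1** sets patient-level liver limits: "Discontinuation of study treatment for abnormal liver tests should be considered by the Investigator when a patient meets one of the conditions mentioned below". The conditions are AST/ALT above 8 x ULN; AST/ALT above 3 x ULN with total bilirubin above 2 x ULN; and a repeat AST/ALT above 5 x ULN.

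**SAP 6.5.3** has one laboratory analysis: "results at each visit and change from screening will be summarized overall and by treatment group using descriptive statistics", namely N, mean, median, SD, quartiles, minimum and maximum. SAP Section 7 turns this into two tables, 3.3.1 for hematology and 3.3.2 ("Summary of biochemistry, Safety population"). None of Listings 1 to 10 is a laboratory listing.

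**SAP Section 1** settles which text governs where descriptions differ: "the SAP will supersede the protocol".

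**The concern.** The safety objective in both documents compares the active doses with placebo, and the study is also meant to inform the Phase 3 dose. Liver limits apply to individual patients, and one of them needs two analytes raised in the same person. A table that takes each analyte separately is not built to answer that.

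The protocol foresaw patient-level outputs. The SAP lacks them, its revision history gives no reason, and its precedence clause means that Protocol 8.5 cannot be relied on to bring them back. The SAP does use category counts elsewhere: SAP 6.5.4 counts patients by SpO2 category, including below 90%, the level that triggers a telemedicine assessment in Protocol 7.4.1. The liver limits, which bear on stopping treatment, get no such count.

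At stake is whether the report can say how many patients in each dose group, and on placebo, went beyond the trial's own liver limits.

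**Working it through.** The documents state no figure on this point, so there is nothing to reproduce. The check compares planned outputs and then tests what the planned statistics can recover.

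**Step 1. Outputs side by side**

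| Laboratory output | Protocol 8.5 | SAP 6.5.3 and Section 7 |
|---|---|---|
| Values and changes, descriptive | Yes | Yes (Tables 3.3.1, 3.3.2) |
| Shift tables by arm | Yes, where applicable | None |
| Counts of clinically significant abnormal values | Yes, where applicable | None |
| Laboratory listing | Not mentioned | None |

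**Step 2. What the planned maxima can show.** All three liver conditions need AST/ALT above at least 3 x ULN. If an arm's AST and ALT maxima at every scheduled visit are at or below that, no scheduled result there met any condition. If its bilirubin maxima are at or below 2 x ULN, no scheduled result met the combined condition. The reader would need the laboratory's ULN, which the documents do not give. Once a maximum exceeds a limit, it shows that at least one patient crossed, but not how many. It also does not show whether a value was a repeat.

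**Step 3. The combined rule.** Take two arms of 52 (the planned arm size). Assumed, not from the documents: ULN 40 U/L for ALT and 20 umol/L for bilirubin, so the limits are 3 x 40 = 120 and 2 x 20 = 40. In both arms, 50 patients have ALT 25 and two have 160; 50 have bilirubin 10 and two have 50. In arm A the same two patients carry both elevations. In arm B they are different patients.

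- ALT mean, both arms: (2 x 160 + 50 x 25)/52 = 1570/52 = 30.19. Median 25, SD 26.21, Q1/Q3 25/25, minimum 25, maximum 160.
- Bilirubin mean, both arms: (2 x 50 + 50 x 10)/52 = 600/52 = 11.54. Median 10, SD 7.77, Q1/Q3 10/10, minimum 10, maximum 50.
- Patients meeting the combined rule: 2 in arm A, 0 in arm B.

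If every screening value was 25 and 10, the change-from-screening summaries are identical too. Per-analyte statistics therefore cannot recover the joint count once both maxima exceed their limits.

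**Step 4. How often a count would be non-zero.** The chance of at least one crossing patient in an arm of 52 is 1 - (1 - p)^52. The crossing rate p is not in the documents, so a range is shown:

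| Assumed p | Chance of at least one in 52 |
|---|---|
| 0.5% | 23% |
| 1% | 41% |
| 2% | 65% |
| 5% | 93% |

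A count of zero also informs: 0 of 52 gives a one-sided 95% upper bound of 1 - 0.05^(1/52) = 5.6%.

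**Step 5. Timing.** SAP 5.3 schedules laboratory tests at screening, Day 10 and Day 28, and dosing runs from Day 1 to Day 10. A crossing first found at a scheduled post-baseline test comes as dosing ends or after it. It would therefore seldom appear among events leading to discontinuation. Crossings earlier in dosing would come from unscheduled tests. SAP 5.3 allows for these, but SAP 6.5.3 gives no rule for summarizing them.

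**The case against.** The strongest reply has four parts.

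- **The protocol's commitment is conditional.** Both outputs are for specific tests where applicable, no test is named, and clinical significance is not defined. Nor does Protocol 8.5 promise a count against each liver limit; Protocol 4.4.2.1 gives prompts for considering discontinuation, not reporting thresholds. This stands as a limit on what was promised. But the qualifier allows a choice of analytes. It does not explain dropping both outputs for every analyte, including the liver tests.
- **Other outputs carry information.** Maxima can exclude crossings at scheduled visits (Step 2). The tables of severe events and of events leading to discontinuation, Listing 9, the reasons for interruption or discontinuation in SAP 6.5.1 and Listing 6 may show individual cases. This stands, but the event and discontinuation outputs depend on what the investigator records. None of these sources gives a count per arm against the limits.
- **Scheduled testing rarely coincides with dosing,** so the discontinuation limits will seldom act on scheduled results. This stands too. It affects what the counts mean, not whether they can be had.
- **Nothing is irrecoverable.** The DMC reviews safety throughout, no formal safety testing is planned, and central laboratory data are transferred electronically, so counts could be produced later. This stands, and it limits the severity.

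A reader might infer that arm means would hide severe cases. Under assumed values (ULN 40, other patients at 30 U/L), one patient at 320 raises the mean by (320 - 30)/52 = 5.6 U/L, and three at 120 raise it by 3 x (120 - 30)/52 = 5.2. But the planned maxima, 320 and 120, separate those two pictures. The comparison of means does not support the point.

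**Conclusion.** The point holds in bounded form. The SAP drops, without explanation, two laboratory outputs that the protocol plans conditionally, and adds no laboratory listing. Followed as written, it yields no per-arm number of patients beyond the Protocol 4.4.2.1 AST/ALT limits. When AST/ALT and bilirubin maxima both exceed their limits, it cannot show whether the elevations fell in one patient. That follows from the text of the two documents; only Steps 3 and 4 rest on assumed values, and they serve as illustration.

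A reader might go further and conclude that the report could not say whether any patient met a liver condition, or that liver injury would go unseen. The documents do not support that, because the maxima and the event outputs can sometimes answer the question. Nor do they support treating eGFR below 50 as an on-treatment safety limit: in Protocol 4.2 and 4.4.2 it is an entry criterion and a rule about screening laboratory results.

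This should be corrected before the analysis. It does not threaten the trial's validity.

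**What to change.** In SAP 6.5.3 and Section 7, by arm:

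1. Restore shift tables from screening for the liver and renal analytes.
2. Report the number and percentage of patients with any post-baseline result, unscheduled results included, beyond each limit already in Protocol 4.4.2.1: AST/ALT above 8 x ULN; repeat AST/ALT above 5 x ULN; and AST/ALT above 3 x ULN with total bilirubin above 2 x ULN in the same patient.
3. Add a listing of patients with out-of-range laboratory results.

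If a post-baseline count of eGFR below 50 is wanted, label it as reusing the entry and screening limit.

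The cost is SAP wording and a small amount of programming, largely on central laboratory data that the SAP already receives. No new samples or visits are needed, and the protocol's limits stay unchanged.

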### 6.5.4 Other Safety Parameters

Vital signs [pulse oximetry and peripheral oxygen saturation] at each visit will be summarized overall and by treatment group using descriptive statistics (N, mean, median, standard deviation, Q1, Q3, minimum and maximum). Change from Day 1 will also be presented similarly using descriptive statistics since Day 1 corresponds to the date of first dose.

In addition, saturation will be characterized as: [<90%], [91%-95%], [>95%] at each visit overall and by treatment group. Number and proportion of subjects within each category will be provided.

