### **Diagnosis and criteria for inclusion and exclusion:**

The following are the inclusion criteria:

1. Willing and able to provide informed consent
2. Male or female patients > 18 years of age on the day of informed consent
3. Have received a confirmed diagnosis of COVID-19 (positive for SARS-CoV-2), as assessed by PCR or point-of-care within 72 hours of first dose on Day 1
4. Have mild to moderate signs or symptoms of COVID-19 with onset within 5 days of first dose on Day 1, at least two of the following symptoms:
  - stuffy or runny nose
  - sore throat
  - shortness of breath
  - cough
  - fatigue
  - myalgia
  - headache
  - chills or shivering
  - feeling hot or feverish
  - nausea
  - vomiting
  - diarrhea
  - anosmia
  - ageusia

5. Outpatient with COVID-19 disease (not requiring oxygen therapy [WHO COVID-19 Clinical Improvement Ordinal Scale, score of 3])
 
6. Patient is aware of the investigational nature of this study and willing to comply with protocol treatments, blood tests, and other evaluations listed in the ICF.

--

The following are the exclusion criteria:

- 1. Females who are pregnant (negative pregnancy test required for all women of child-bearing potential at Screening) or breast-feeding
- 2. Male patients and women of childbearing potential (women who are not surgically sterile or postmenopausal defined as amenorrhea for >12 months) who are not using at least one protocol-specified method of contraception
- 3. Severe COVID-19 disease as defined by the WHO COVID-19 Clinical Improvement Ordinal Scale, scores of 5 (non-invasive ventilation or high-flow oxygen), 6 (intubation and mechanical ventilation), or 7 (ventilation + additional organ support pressors, renal replacement therapy [RRT], extracorporeal membrane oxygenation [ECMO])
- 4. Expected survival less than 72 hours
- 5. Peripheral capillary oxygen saturation (SpO2) <90% while breathing room air
- 6. Treatment with other drugs thought to possibly have activity against SARS-CoV-2 infection like remdesivir, favipiravir, within 7 days prior to enrollment or concurrently
- 7. History of abuse of drugs or alcohol that could interfere with adherence to study requirements as judged by the Investigator
- 8. Use of any other concurrent investigational drugs while participating in the present study

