## **7.2. Safety and Tolerability Assessments**

### **7.2.1. Adverse Events**

Adverse event definitions, assignment of severity and causality, and procedures for reporting SAEs are detailed in [Appendix 1](#).

The condition of each patient will be monitored from the time of providing informed consent to completion of study participation. Patients will be observed for any signs or symptoms and asked about their condition by open questioning, such as “How have you been feeling since you were last asked?” at each patient contact. Patients will also be encouraged to spontaneously report AEs occurring at any other time during the study.

Any AEs and remedial action required will be recorded in the patient’s source data. The nature, time of onset, duration, and severity will be documented, together with an Investigator’s (or designee’s) opinion of the relationship to study drug.

AEs recorded during the course of the study will be followed up, where possible, until resolution or until the unresolved AEs are judged by the Investigator (or designee) to have stabilized. This will be completed at the Investigator’s (or designee’s) discretion.

For any participants who require hospitalization, if possible, study drug should be continued and an effort made to collect study-related data and conduct End of Study procedures. Every attempt should be made for a visit to be scheduled after discharge from the hospital, providing that the visit is within 28 days of initiation of dosing, or to visit the patient in the hospital, where permitted. In lieu of a study visit, study site staff should obtain equivalent data from hospital records. Pertinent information from hospitalization will be collected, including need for

supplemental oxygenation, mechanical ventilation, days of hospitalization and ventilation, and death.

Serious AEs of worsening COVID-19, with the exception of death, will be considered disease progression and will not be collected for the safety database.

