## **7.4. Vital Signs, Physical Examination, and Other Safety Evaluations**

### **7.4.1. Vital Signs**

Pulse oximetry will be measured as a safety assessment, with saturation <90% triggering a telemedicine assessment.

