- a. Screening/Baseline assessments may all be performed on the same calendar day and should be performed at the study site or as a home visit within 72 hours of first dose. Baseline assessments that are also performed at Screening do not need to be repeated if on the same calendar day. Study drug should be dispensed at the Screening/Baseline visit and only taken after the Day 1 virtual visit confirming the positive COVID-19 test has occurred. If the PCR test is negative or laboratory results exclude the patient, they will not take the first dose of study drug and be withdrawn from the study.
- b. Patients will be randomized to receive either 900, 1800, or 3600 mg of dalcetrapib treatment or placebo.
- c. The entry testing is performed locally based on testing methods available at the site, such as PCR or rapid antigen test.
- d. Patients must have at least two mild to moderate signs or symptoms of COVID-19, as described in the inclusion criteria, with onset within 5 days of first dose on Day 1. Symptoms will be assessed daily for the first 10 days, then at Day 14 and Day 28 and as clinically indicated.
- e. Dates of change in WHO scale status between visits will be recorded over the course of the 28-day study period.
- f. SARS-CoV-2 viral loads will be obtained by both saliva (Oragene) and mid-turbinate nasal swab self-collected under supervision of a healthcare professional at Screening/Baseline, Day 1, Day 3, Day 5, Day 7, Day 10, and Day 28.
- g. Two PK samples will be collected on Day 10, one at predose and one at postdose in a sampling window of 0-2, 2-4, 4-6, 6-10, or 10-24 hours postdose. Patients will be evenly randomized to one of the sampling windows on Day 10.
- h. Study drug is self-administered as once daily oral tablets on Days 1 to 10.
- i. In case of screen failure only.

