#### 5.4 Other Safety Parameters

Pulse oximetry and saturation measurements will take place on screening, Days 1, 3, 5, 7, 10, follow-up visit 1 (Day14) and follow-up visit 2 (Day28/EOS).

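### The SpO2 tables do not separate readings taken on supplemental oxygen or ventilation, so a patient who has worsened can appear in a normal category with a rise from Day 1

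*SAP*

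**What the plan says.** SAP 6.5.4 sets out three displays of oxygen saturation in the Safety population: descriptive statistics at each visit ("Vital signs [pulse oximetry and peripheral oxygen saturation] at each visit will be summarized overall and by treatment group using descriptive statistics"), change from Day 1, and bands, where "saturation will be characterized as: [<90%], [91%-95%], [>95%] at each visit overall and by treatment group". The table list in SAP section 7 has one continuous SpO2 table (numbered 3.4.1, a number it shares with the pulse-rate table) and Table 3.4.2, "Summary of vital SpO2 (%) in categories, Safety population". None of these refers to oxygen use.

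Measurement runs through the whole study. SAP 5.4 states "Pulse oximetry and saturation measurements will take place on screening, Days 1, 3, 5, 7, 10" and continues to Days 14 and 28. Protocol 7.4.1 gives the purpose: "Pulse oximetry will be measured as a safety assessment, with saturation <90% triggering a telemedicine assessment". It does not say whether the reading is on room air. The only room-air condition in either document is exclusion criterion 5 in the protocol synopsis and section 4.2: "Peripheral capillary oxygen saturation (SpO2) <90% while breathing room air".

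Hospitalized patients remain in follow-up. For them protocol 7.2.1 says "In lieu of a study visit, study site staff should obtain equivalent data from hospital records".

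**The concern.** A saturation reading is interpretable only if one knows what the patient was breathing. Inclusion criterion 5 admits outpatients who do not need oxygen, so the Day 1 value is in effect a room-air value. A later reading on nasal prongs, high flow or a ventilator is a different quantity, yet SAP 6.5.4 subtracts one from the other and bands both on the same scale.

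The patients whose respiratory state this safety table should show are thus the ones it can misclassify. An arm with more patients on oxygen could look no worse, or slightly better, than placebo on SpO2. The SAP does treat intervention as informative elsewhere: under SAP 6.2.2.2, a patient who has received another antiviral is given the maximum symptom score instead of the observed one. SpO2, which oxygen changes directly, has no corresponding rule.

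**Working it through.** The plan states no figure on this point, so there is nothing to reproduce. The check has two parts: whether such readings can enter the tables, and how far they could move them.

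**Can they enter?**
- Oximetry is scheduled at every visit to Day 28 (protocol Appendix 4; SAP 5.4).
- Protocol 7.2.1 provides for visiting a hospitalized patient or taking equivalent data from hospital records.
- SAP 6.5.4 excludes and flags nothing.

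A reading on oxygen that reaches the dataset is therefore tabulated like any other.

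**One patient.** Exclusion criterion 5 removes only values below 90%, so a patient may enter at 91%. Suppose that patient worsens and reads 97% on oxygen (assumed). Change from Day 1 = 97 − 91 = +6 points, and the category moves from [91%-95%] to [>95%]. A reading of 94% on oxygen would fall in [91%-95%].

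**An arm at one visit.** Inputs:
- n = 52 patients per arm (SAP 2.1), all assumed to have a reading.
- k = number on oxygen at that visit (assumed).
- Saturation those patients would have on room air, R = 85 to 88% (assumed).
- Saturation on oxygen, S = 94 to 97% (assumed).

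Shift in the arm mean = k × (S − R) / n. Share moved out of the band below 90% = k / n. The smallest gap is 94 − 88 = 6 points and the largest is 97 − 85 = 12 points.

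| k | Shift in mean, low | Shift in mean, high | Moved out of <90% |
|---|---|---|---|
| 1 | 1 × 6/52 = 0.12 | 1 × 12/52 = 0.23 | 1/52 = 1.9% |
| 3 | 3 × 6/52 = 0.35 | 3 × 12/52 = 0.69 | 3/52 = 5.8% |
| 5 | 5 × 6/52 = 0.58 | 5 × 12/52 = 1.15 | 5/52 = 9.6% |

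With one to three patients the mean moves by tenths of a point. The band counts, the minimum and the individual changes are affected more.

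**Would dropping the on-oxygen readings cure the mean?** No. Take 47 patients at 97% on room air and five at 96% on oxygen (assumed). All readings: (47 × 97 + 5 × 96)/52 = 5,039/52 = 96.9%. Room air only: 97.0%. Leaving out the sickest patients raises the mean further. A room-air summary is useful only if it is labelled as such and shown with the number left out.

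The bands also leave a reading of exactly 90% unassigned. That is a separate matter and does not affect this point.

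**The case against.** The strongest reply is that oxygen use is reported by arm elsewhere. SAP 6.4.3.7 gives the number, percentage and type of oxygen therapy through Day 28. SAP 6.4.3.5 shows the WHO scale by visit, where protocol Table 4 assigns score 4 to mask or nasal prongs and 5 to 7 to higher support. SAP 6.5.2.2 counts serious events requiring oxygen, ventilation or ECMO. The SpO2 tables are descriptive, and SAP 6.5 plans no formal safety testing.

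This largely stands. A reader might infer that the plan conceals respiratory deterioration, or that every patient on oxygen is counted as normal. The documents support neither reading. The first is answered by the outputs just listed. The second depends on the value reached on oxygen and on a reading being taken at that visit.

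The reply is not complete. The oxygen-progression endpoint is taken from the Adverse Event form (SAP 4.2), and the serious-event rows rest on adverse event data too. Protocol 7.2.1 says serious events of worsening COVID-19, other than death, are not collected for the safety database, so both routes may undercount. The WHO scale does not depend on that rule, but it is an ITT efficacy display with no Day 7 comparison.

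A second reply is that few such readings may exist. The hospital items that protocol 7.2.1 names are oxygen need, ventilation, days and death; SpO2 values are not among them. Appendix 4 lets later visits be held by telephone and does not count assessments missed at phone visits as deviations. Protocol 3.1 speaks of following hospitalized patients for vital status, where the synopsis and SAP 2.1 say safety assessment. This also stands: the number of affected readings cannot be worked out from the documents, nor can one tell whether the eCRF records oxygen status with each reading.

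**Conclusion.** The point holds for the SpO2 displays and goes no further. As SAP 6.5.4 is written, a patient who worsens and is put on oxygen can be counted in [91%-95%] or [>95%] and can show an apparent rise from a Day 1 value taken without oxygen. The SpO2 tables alone can therefore misstate respiratory status.

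The size is unknown. The figures of 0.12 to 0.69 points for one to three patients rest on assumed saturations, an assumed number of patients on oxygen at the same visit, and a full 52 readings per arm. A large masked contrast between arms would need several patients in one arm to be on oxygen at the same visit, all below 90% without it and all corrected into the top band, with no low reading recorded beforehand. Nothing in the documents establishes that. This is a cheap improvement to one descriptive display and does not threaten the trial's conclusions.

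**What to change.** **Table 3.4.2.** Add a category for readings taken on supplemental oxygen or ventilation. Keep all patients with a reading at that visit in the denominator, so that these patients move out of the normal bands and are not dropped.

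**Mean and change from Day 1.** Keep the all-readings summary in SAP 6.5.4 and the continuous SpO2 table. Add a labelled room-air-only summary with the number on oxygen beside it, and a note that it leaves out the sickest patients.

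**Identifying the readings.** State the order in the SAP:
1. Oxygen status recorded with the reading, if the eCRF has it.
2. Otherwise a WHO score of 4 to 7 on that date. Protocol Appendix 4, footnote e, already provides the dates: "Dates of change in WHO scale status between visits will be recorded over the course of the 28-day study period".
3. As a supplement, oxygen use on the Adverse Event form for oxygen given outside hospital, since scores 4 to 7 are inpatient states.

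**Cost.** A few sentences of SAP text, one more row per visit and a small data merge. Some misclassification of home oxygen will remain, because the Adverse Event form item records whether an event required oxygen, not whether oxygen was in use at a given reading. No visit, assessment or clinical rule changes.
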